Several other exclusion criteria were modified for the current protocol. For example, a serum creatinine level of > 2 mg/dl was originally an exclusion criterion. However, this was replaced in the revised protocol by "history of severe kidney or liver failure." In addition, exclusion criteria related to having a history of myocardial infarction, stroke, unstable angina, coronary artery bypass grafting or angioplasty/stenting were changed from the past six months to the past three months, as it was determined by our physician investigators that this would be a sufficient interval to determine medical stability. Exclusionary criteria related to arrhythmia were also changed from "uncontrolled arrhythmia" to "cardiac dysrhythmia (except atrial fibrillation) treated with anti-arrhythmia medications." Additionally, use of current steroid treatment was removed as an exclusionary criterion, while "current use of a medication that may interfere with primary study endpoints or that may increase the risk of side effects from study medication that can not be discontinued" was added.

Several additional exclusion criteria were added to the revised protocol. These included the presence of untreated pheochromocytoma (due to potential risks associated with nicotine and nicotine replacement on the adrenal medulla). Additionally, participants who have valvular heart disease or pulmonary hypertension causing shortness of breath with walking, cycling at a moderate speed, or light housework will be excluded due to concerns regarding an increased risk of a cardiac event from exercise and an inability to modify their physical activity as recommended in portions of the interventions.

In order to increase our potential pool of eligible participants, we also modified the protocol to allow entry of individuals who had quit smoking on their own within the past two to six weeks. Consequently, participants do not need to be smoking upon entry into the study. These individuals can be eligible for random assignment to treatment conditions provided they meet other eligibility criteria including at least two weeks of prolonged abstinence from cigarette smoking.

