Participants will be recruited through community advertising and via referral from their primary care provider. Participants who respond to advertisements or study referrals will be given information about the potential risks and benefits of study participation. Informed consent will be obtained at that time. They also will be questioned for eligibility at this time. Participants who are interested and who meet initial eligibility criteria will be scheduled for a Baseline Visit. The entire length of the study for each participant will be approximately 14 months. Due to the length of the study and number of visits, the participants will be given "Take Home Logs" that will help them keep track of the visit schedule. It is also a place that they can write any adverse events and concomitant medication use, which will help them remember to report the events or medications at the next study visit.

**Baseline (Please note that in order to improve clarity, this visit is referred to as the Screening Visit in the Participant Consent Form)**

Baseline Visits will be conducted at the Preventive Intervention Center. Participants also will be asked for demographic information and to complete a medical history form. All of the inclusion/exclusion criteria will be reviewed. A brief physical exam will be performed for participants who have not seen his/her regular primary care provider in the past 3 years or who do not have a regular primary care physician. In addition, vitals will be taken (height, weight, pulse, and blood pressure). Waist circumference will also be measured. Percentage of body fat will be measured using a bioelectrical impedance analysis, which involves briefly stepping on a scale-like device. Adverse events and concomitant medications will be recorded. Because NRT is not FDA-approved for use during pregnancy, any female participant who has the potential to be pregnant will be given a urine pregnancy test.

Participants will be questioned about any recent symptoms provoked by moderate intensity physical activity (e.g., walking, cycling at a moderate speed, general housework). Specifically, we will use the Physical Activity Readiness Questionnaire (PAR-Q) and the Rose Angina Questionnaire to assess major signs and symptoms of cardiovascular disease (e.g., angina) in order to ensure that the intervention does not place participants at increased risk for a cardiac event.

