#### Randomization

Following the smoking cessation sessions, all participants who are abstinent from smoking based on two-week prolonged abstinence criteria will come in for a randomization visit (Please note that in order to improve clarity, this visit is referred to as the Group Assignment Visit in the Participant Consent Form). The participant will be asked to report their current smoking status, followed by an expired air carbon monoxide (CO) assessment. For those who fail the CO test (i.e., CO > 10 ppm), yet still claim to be abstinent from smoking, a salivary cotinine test will be given to provide a confirming/disconfirming assessment. For those who fail the CO test but report using a nicotine replacement therapy (which would alter the results of the salivary cotinine test) will instead be tested for thiocyanate via blood draw. Participants who do not successfully quit smoking will be given a chance to recycle through the smoking cessation intervention a second time.

At this visit the study staff will perform an interval medical history with the participant, to ensure nothing critical has changed from the screening visit. Vitals will also be taken again (weight, pulse and blood pressure). Waist circumference will also be measured. Percentage of body fat will be measured using a bioelectrical impedance analysis. Inclusion/exclusion criteria will be reviewed again. Adverse events and concomitant medications will be reviewed. The participant will have an electrocardiogram (ECG) performed by study staff and reviewed by a physician for evidence of 2nd or 3rd degree AV block and to assess for previous silent myocardial infarction. If the ECG results are inconclusive, the participant will be advised to consult his/her primary care provider and will not be able to participate in the study. If the participant is still interested in participating in the study, he/she should contact his/her primary care provider in order to perform an exercise stress test. The test would be conducted under the supervision of the primary care provider. If the results of the exercise stress test indicate that it is safe for the individual to enroll in the study, and the primary care provider and the

study physician clear them for participation, then they will be allowed to enroll provided they meet other eligibility criteria.

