Participants will be asked to complete a brief (7-item) questionnaire to assess the extent to which they learned and retained key information provided in the smoking cessation intervention, and to provide their impression of the helpfulness of various parts of the intervention.

Any female participant who has the potential to be pregnant will be given a urine pregnancy test. Those participants that are abstinent from smoking and meet all other criteria will be randomized to one of three treatment conditions.

Lastly, participants will be instructed to test five overnight urine samples at home using chloride titrator sticks in order to measure baseline dietary sodium intake. Urinary chloride provides a good option for estimating dietary sodium intake, and is less participant burden than collecting 24 hour samples. Participants will be instructed to collect overnight urine samples (2200 to 0600) each morning in containers provided by the study laboratory. Participants will then place a chloride titrator stick into the urine sample for a period of 20 minutes. Each test strip has a capillary column containing

silver dichromate that forms silver chloride when reacting with chloride ions. After the column becomes saturated, a moisture sensitive signal appears at the top. A line appears on the column providing a value ranging from 0.0 to 10.0. The participant will mark the titrator stick reading on a chart provided by the study staff. Participants will be instructed to measure overnight urinary chloride levels for five days, as this is the number of samples recommended to ensure an accurate estimate of mean sodium intake. After five overnight samples the participant will mail or fax the chart back to the study staff.

The randomization visit will take approximately 2 hours to complete, plus the participant's at-home time collecting overnight urine samples.

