**VII.E.9**

***Will subjects be provided any compensation for participating in this study?***

	Yes
VII.E.10	Cash/check
	Yes
VII.E.16	Other
	No
VII.E.19	Describe the compensation plan including
	
 
• Compensation amount and type per visit
 
• Total compensation
 
• Pro-rating for early withdrawal from study
 
 
A participant can receive up to \$100 for participation in the study. This money is for the time spent in this study. If the participant starts the study but stops before finishing the study, he/she will receive part of this money based on which visits have been completed. Partial payment will be made as follows:
 
Completion of Screening Visit = \$25
 
Completion of Screening and Group Assignment Visit = \$25, (\$50 total)
 
Completion of Screening, Group Assignment, and 6 Month Follow Up Visits = \$25 (\$75 total)
 
Completion of Screening, Group Assignment, 6 Month, and 12 Month Follow Up Visits = \$25 (\$100 total)
 
 
• Please note: Participants who do not quit smoking during the smoking cessation portion of the study are not eligible to continue in the study (to the group assignment visit, interventions, or follow up visits). However, we ask that they complete a short phone interview at the 6 and 12 month time points. For those phone visits they will be compensated \$10 (compared to \$25 for the in-clinic follow up visit).
 
 
Participants that enter the study who have already quit smoking on their own, have the screening and group assignment visit combined. Those such participants would receive \$50 for completing that joint screening/group assignment visit. After that, the payment for the rest of the study is the same as above, with the total compensation for completing all visits equaling \$100.

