Data Analytic Plan

Study Title: Blood Pressure Control in Hypertensive Smokers

NCT: NCT00113074

Approval Date: 09/20/2021

Treatment and Prevention Study Data Analytic Plan

Overview:

The main statistical analyses will be for the three-group randomized clinical trial with the primary analyses restricted to participants that do not relapse to smoking. Participants who discontinue study participation will be assumed to have relapsed to smoking. Therefore, analyses will be restricted to those with available data.

The primary efficacy endpoints are BP and body weight. Since the aim is to evaluate long-term efficacy, the primary analysis will evaluate treatment effects at 1-year. Analyses will also be conducted to assess changes in BP and body weight at six months. The primary analysis will be restricted to participants that have not relapsed to smoking and who provide follow-up data. Secondary analysis will be performed using all participants. The primary analysis will be performed using ANCOVA to assess for treatment effects adjusting for the baseline value of the dependent variable, study site, and any baseline variables found to differ significantly between groups. In all cases, each of the two experimental groups will be compared to the UL group. Since there are two pair-wise treatment comparisons of interest (BPC vs. UL; WGP vs. UL), we will utilize Fisher's least significant difference (LSD) approach to protect against inflation of the experimentwise error rate. An initial omnibus test will be used to test the null hypotheses that all group means are equal. Rejection of the null hypothesis will result in subsequent pair-wise comparisons between treatment groups. Conversely, if the null hypothesis associated with the omnibus test is not rejected, pair-wise comparisons will not be necessary.

Secondary endpoints will include servings of fruits and vegetables per day, dietary fat intake (% of total energy from fat), overnight urinary chloride excretion (mmol/day), and self-reported physical activity (kcal/kg/day). The analyses for the secondary endpoints will be similar to that for the primary endpoints, with groups compared using ANCOVA to assess for treatment effects adjusting for baseline values, study site, and baseline variables found to differ significantly between groups. In all cases, each of the two experimental groups will be compared to the UL group.

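### The primary ANCOVA adjusts for one baseline BP or weight without naming the visit; anchor it at randomization and add the screening value as a second covariate

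*SAP*

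**What the plan says.** The primary model in the SAP Overview, repeated in protocol XI.1, compares groups at one year "adjusting for the baseline value of the dependent variable", study site, and any baseline variables that differ significantly between groups. Neither text ties the baseline value to a visit.

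Protocol VII.E.6 describes two visits before allocation:

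- **Baseline** (called the Screening Visit in the consent form), before the quit date: "vitals will be taken (height, weight, pulse, and blood pressure".
- **Randomization** (the Group Assignment Visit), after two weeks of abstinence: "Vitals will also be taken again (weight, pulse and blood pressure".

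Section C.2 also admits "individuals who had quit smoking on their own within the past two to six weeks". Under the compensation plan (VII.E.19) these participants "have the screening and group assignment visit combined", so they have one pre-allocation value, taken after quitting.

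The word baseline is not used consistently. It names the first visit, yet the urinary chloride sticks issued at the randomization visit are there "in order to measure baseline dietary sodium intake".

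**The concern.** Two analysts could follow this SAP and fit different primary models. One would take the covariate from the visit named Baseline. For cessation-phase participants that is a value recorded while smoking, about four weeks or more before allocation: Session 1 comes about one week after Baseline, and Session 4 three weeks after quitting. It is earlier still for those who repeat the program. For self-quitters it is a post-quit value. The other analyst would take the randomization-visit value, which is post-quit for everyone.

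The protocol's background (A.2) expects cessation itself to raise weight and possibly BP. The two candidates can therefore differ systematically, and so can any within-arm change reported from them.

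There is also a possible gain. BP is a noisy outcome, and a second pre-allocation reading already exists for everyone who went through the cessation phase. A model with a single baseline leaves one of the two readings out.

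**Working it through.** **1. The plan's own figure.** Inputs from protocol XI.2: SBP difference 5.3 mmHg, SD of change 14.5; DBP 3.4 and 9.4; weight 2.0 kg and 5.0 kg; two-sided alpha 0.025; power 80%. With n = 2·SD²·(z₀.₉₈₇₅ + z₀.₈₀)²/d², the results per group (normal, then t) are:

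- SBP: 143 and 144, against 144 stated.
- DBP: 146 and 147, against 147 stated.
- Weight: 119 and 121, against 120 stated.

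Power at n = 145 is 80.8% for SBP, 79.9% for DBP and 87.8% for weight (87% stated). The sample size reproduces. It rests on change scores and uses no correlation.

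**2. Effect of a second pre-allocation value for SBP.** The documents give no correlation, so ρ is an assumption. With equal variances σ² and one common correlation ρ between any two visits:

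- change-score variance = 2σ²(1−ρ)
- ANCOVA residual variance, one baseline = σ²(1−ρ²)
- ANCOVA residual variance, both = σ²(1−2ρ²/(1+ρ))
- ratio of both to one = (1+2ρ)/(1+ρ)²

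Holding the change-score SD at 14.5, the residual SD with one baseline is 14.5·√((1+ρ)/2). At ρ = 0.5 that is 14.5·√0.75 = 12.6. The ratio is 2/2.25 = 0.889.

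| ρ | Fall in residual variance | n per group, one → both | SBP power at 145, one → both |
|---|---|---|---|
| 0.3 | 5% | 93 → 88 | 94.7% → 95.8% |
| 0.5 | 11% | 107 → 95 | 91.2% → 94.2% |
| 0.7 | 17% | 121 → 101 | 87.2% → 92.8% |
| 0.9 | 22% | 136 → 105 | 82.9% → 91.7% |

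**3. Self-quitters contribute no second value.** Their share is not stated; the attrition plan in XI.2 counts all 570 planned randomizations as coming from the cessation phase. With share s, the fall is roughly (1−s) times the figure above. At s = 30% it is 0.7 × 11.1% = 7.8% at ρ = 0.5, and 0.7 × 17.0% = 11.9% at ρ = 0.7.

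A simulation (145 per arm, 4,000 replicates, self-quitters with the randomization value only) compared the randomization value alone with both values plus an indicator. The SE of the SBP difference went from 1.48 to 1.43 (ρ = 0.5, 10% self-quitters), 1.55 to 1.44 (ρ = 0.7, 10%) and 1.58 to 1.50 (ρ = 0.7, 30%). Every covariate choice was unbiased: mean estimates ran from −5.27 to −5.36 against a true −5.3.

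**4. The visits need not be exchangeable.** Let r₁ and r₂ be the correlations of the screening and randomization values with the outcome, and r_b their correlation with each other. Then R² = (r₁² + r₂² − 2r₁r₂r_b)/(1−r_b²).

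- BP, r₁ = 0.36, r₂ = r_b = 0.60: residual variance 0.64 with one or both, so no gain. Here the earlier value acts only through the later one.
- BP, r₁ = 0.50, r₂ = r_b = 0.60: 0.64 falls to 0.609, a gain of about 5%.
- Weight, 0.9025/0.95/0.95 (r₁/r₂/r_b): no gain. 0.94/0.95/0.98: about 2%. 0.95/0.95/0.98: about 9%.

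**5. Cost of mixing two kinds of baseline.** If cessation shifts the covariate by δ, the added residual variance is about s(1−s)ρ²δ², set against σ²(1−ρ²). With assumed s of 10 to 30%, δ of 2 to 5 mmHg and ρ of 0.5 to 0.7, this runs from 0.09 × 0.25 × 4/157.7 = 0.06% to 0.21 × 0.49 × 25/178.7 = 1.4% for SBP. For weight, with a slope near 1, a 1 to 2 kg shift and the planned variance of 25 kg², it is 0.09 × 1/25 = 0.4% to 0.21 × 4/25 = 3.4%.

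**The case against.** The strongest reply is that the plan merely leaves a visit unnamed and discards nothing. A reader might infer from the visit label that the randomization-visit reading goes unused. The documents do not establish that. The physical activity questionnaire and both dietary screeners are first given at the randomization visit, so for those secondary endpoints baseline can only mean that visit. If BP and weight follow the same usage, every participant already has a post-quit baseline and nothing is mixed. The chloride wording alone is weaker support, because the same phrase recurs under Follow-up Visits. This objection stands: the mixed baseline is one reading of the plan, not a stated feature.

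A reader might also think that using both readings cures the self-quitter problem. It does not, because self-quitters have no pre-quit value. Fixing the reference at randomization is what gives baseline a single meaning.

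Nor may 11 to 17% be taken as the expected gain. It assumes exchangeable visits and no self-quitters, yet the visits straddle cessation and possibly patch use. Finally, power with one reading already exceeds the 80% target under the plan's inputs, and mixing costs little by the figures in step 5. What remains is a needed definition, plus a refinement that uses data already in hand.

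**Conclusion.** The point holds as an undefined covariate with a low-cost improvement available. It is not an error of validity or of sample size: a single-baseline ANCOVA is valid whichever visit is used, and the planned figures reproduce.

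The definition is needed whatever the gain in precision, since the primary estimate depends on it. For BP, the fall in residual variance from the second covariate lies anywhere from 0 to about 20%. The narrower 11 to 17% (no self-quitters) and about 8 to 12% (30% self-quitters) rest on an assumed common correlation of 0.5 to 0.7. For weight the gain may be near zero. The correlations and the self-quitter share are all assumptions. That most participants have two values is an inference from the planned flow, not a stated count.

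**What to change.** State in the SAP that, for BP and weight, baseline is the randomization-visit value for all participants. Add the screening-visit value, where it was taken at a separate visit, as a second covariate, with an indicator for participants whose visits were combined. For these participants set the screening value either to a constant or to the combined-visit value, and say which. The simulation above did the latter: it entered the screening-minus-randomization difference as zero. Without such a rule, a two-covariate model would drop self-quitters as incomplete cases. Use the same definition for the six-month analyses and the secondary analysis of all participants.

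The cost is a few lines of text and about two degrees of freedom per model, with no new data. Protocol VII.A.4 reports data collection complete and the SAP is dated 09/20/2021, so this is a late modelling choice. It should be dated, and recorded as made without sight of results by arm.

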#### A.2. Weight Gain Following Smoking Cessation

Although smoking cessation should be a top priority for those with hypertension, quitting smoking leads to a nontrivial weight gain, potentially exacerbating their already high blood pressure. Considering that body weight is the strongest single predictor of BP (McCarron & Reusser, 1996) and that even small weight gains (e.g., 5 kg) are associated with an increased risk of developing hypertension (Field et al., 1999; Huang et al., 1998; Vasan et al., 2001), it is not surprising that postcessation weight gain may have an adverse impact on BP. Indeed, several prospective observational studies have demonstrated a significant increase in BP following smoking cessation (Jenner et al., 1988; Lee et al., 2001; Seltzer, 1974). Furthermore, smoking cessation has been associated with an increase in the prevalence of hypertension in some studies (Gerace et al., 1991; Lee et al., 2001). These increases in BP following smoking cessation appear to be largely, although not totally, the result of postcessation weight gain (Gerace et al., 1991). Together, this body of literature suggests that, although smoking cessation is associated with numerous health benefits for smokers with elevated BP, the weight gain associated with quitting may lead to increases in BP, which may carry additional cardiovascular risk.

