## VI. Subjects

VI.1 **How many adult subjects do you expect to consent or enroll for this project?**  
912

VI.2	What is the age of the youngest adult subject?
	18.0
VI.3	What is the age of the oldest adult subject?
	75.0
VI.4	What is the percentage of adult male subjects?
	50
VI.5	What is the percentage of adult female subjects?
	50
VI.6	How many minor subjects do you expect to consent or enroll for this project?
	0
VI.13	Describe EACH of your subject populations

- **Include description of any control group(s)**
- **Specify the Inclusion/Exclusion criteria for EACH group**

Participants will be cigarette smokers with elevated Blood Pressure (BP) who smoke at least five cigarettes per day. Patients will be eligible if their BP is in the Prehypertensive (120-139/80-89 mm Hg) or Stage I hypertensive (140-159/90-99 mm Hg) range based on JNC 7 criteria (Chobanian et al., 2003). However, we will exclude patients who are Stage II hypertensive ( $> 160/100$  mm Hg). We will include patients who are using antihypertensive medications, provided their BP is not out of control (i.e.,  $> 160/100$  mm Hg), but will record medication, dose, and frequency so that these can potentially be adjusted for in the analyses.

We also will enroll former smokers who recently quit smoking on their own. Former smokers will be eligible if they have quit smoking in the past two to six weeks.

Participants who enroll in the study who are already abstinent will not take part in the smoking cessation portion of the intervention (described below).

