## **XI.2**

### ***Provide the rationale or power analysis to support the number of subjects proposed to complete this study.***

This study is a multi-site, randomized clinical trial, with study sites in Iowa City, IA, Rochester, MN, and Memphis, TN. The sample size calculations provided below reflect the target number of participants for the entire trial, across each of the three sites. Only subjects that meet criteria for tobacco abstinence at the end of the 4-week smoking cessation phase will be eligible for randomization, and of these participants, only those that meet criteria for prolonged abstinence through 1-year follow-up will be included in the primary analysis. Because methodological factors such as abstinence criteria and length of follow-up can have a significant impact on the primary endpoints, we consulted the extant literature and chose only studies that were fairly similar to the proposed project to obtain estimates for sample-size planning. The majority of these studies present data as change from baseline. For this reason, sample-size calculations for the present investigation are based on an analysis of change scores. However, an alternative to analyzing change scores is to analyze follow-up data using an analysis of covariance model with the baseline value included as a covariate. In addition to adjusting each subject's follow-up score for his or her baseline score, the analysis of covariance approach has the advantage of being unaffected by baseline differences. This approach also typically has greater statistical power to detect a treatment effect than analyzing change scores (Vickers et al. 2001). Therefore, sample-size requirements based on an analysis of change scores will provide similar or greater statistical power for analyses that are performed using an ANCOVA approach.

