Relapse to tobacco use will be analyzed as an exploratory endpoint. At every contact following randomization subjects will be assessed for relapse to tobacco use, with relapse defined as using tobacco on seven consecutive days or using tobacco at least one day per week on two consecutive weeks. This definition is consistent with that proposed by the Society for Research on Nicotine and Tobacco (Hughes et al., 2003). For subjects that relapse, the date of relapse will be defined as the first day of tobacco use in the 7-day or 2-week period. Subjects that discontinue study participation prior to the 1-year follow-up visit, who have not already met relapse criteria, will be assumed to have relapsed to using tobacco. For these subjects, the date of relapse will be assigned as the day following their last study visit. Time to relapse will be analyzed using Cox proportional hazards regression (PROC PHREG) with time to relapse as the dependent variable and intervention group as the independent variable. For subjects that do not relapse to using tobacco, the time to relapse will be censored as of the date of their 1-year follow-up visit. Additional multivariable analyses assessing characteristics associated with relapse to tobacco use will be considered. However, these analyses will be considered exploratory in nature since our ability to perform meaningful multivariable analyses will be dependent on the number of subjects that relapse to tobacco use.

A number of additional analyses will be performed to describe the study characteristics and assess comparability between study groups. Participant adherence will be assessed as percentage of contacts completed and compared between groups using the rank sum test. The percentage of subjects that use other products (or programs) for smoking cessation, blood pressure or weight control will be summarized separately and compared between intervention groups using Fisher's exact test. Changes in hypertension status will be noted and coded as: -1=decrease in status, 0=no change, +1=increase in status; and changes in hypertension medication status will be noted and coded as: -1=decrease in medication, 0=no change, +1=increase in medication. Using these coded variables, changes in hypertension status and medication status will be compared across treatment groups using the Kruskal-Wallis test.

Analyses for phase 1 (smoking cessation):

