Although the primary analyses are for the randomized trial, the first phase of this investigation (open-label smoking cessation phase) will provide meaningful data regarding smoking cessation efforts for individuals. For this phase, the primary outcome will be prolonged tobacco abstinence at the final program session (session 4) defined as self-reported abstinence from all tobacco (not even a puff) for the last 14 days, confirmed by expired CO<10 ppm. The percentage of participants that discontinue the program prior to the 4th session will be summarized along with the reason for discontinuation. The overall abstinence rate at the end of the program will be summarized using a point estimate and 95% confidence interval, with subjects that discontinue study participation assumed to be smoking. In addition, logistic regression will be used to perform exploratory analyses to assess potential participant characteristics associated with abstinence at the end of treatment. Participant characteristics considered in this analysis will include: age (years), gender, smoking rate (cpd), and level of nicotine dependence (FTND).

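### Extra ANCOVA covariates are picked by unspecified baseline significance tests, which select on imbalance rather than prognosis and leave the final model open; the cost is a modest loss of precision

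*SAP*

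**What the plan says.** The SAP Overview and Protocol XI.1 share one text. The primary ANCOVA of blood pressure and body weight at 1 year adjusts for the outcome's baseline value, study site, and "any baseline variables found to differ significantly between groups". The secondary endpoints follow the same rule: "adjusting for baseline values, study site, and baseline variables found to differ significantly between groups". The analysis set is selected after randomization: "The primary analysis will be restricted to participants that have not relapsed to smoking and who provide follow-up data".

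Nothing else in the documents completes the rule:

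- The SAP paragraph meant to "describe the study characteristics and assess comparability between study groups" covers adherence, use of other products, and changes in hypertension and medication status. All of these arise after randomization.
- The exploratory phase 1 logistic model does name its covariates (age, gender, smoking rate and nicotine dependence), but that list is for abstinence, not for the ANCOVA.
- Protocol VI.13 says of antihypertensive drugs that the study "will record medication, dose, and frequency so that these can potentially be adjusted for in the analyses". That is an option, not a specification, and the SAP does not repeat it.
- The 0.025 level appears only in the sample-size section (Protocol XI.2).

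**The concern.** Covariates earn their place in an ANCOVA by predicting the outcome. A test of baseline difference between randomized arms carries no information about that. It selects strong predictors and noise at the same rate, namely the test level. Protocol XI.2 favours ANCOVA partly because "This approach also typically has greater statistical power to detect a treatment effect than analyzing change scores", yet beyond the baseline value and site this rule seldom delivers any further gain.

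The second problem is that the model is not fixed. Two analysts could follow the text faithfully and fit different models, because candidates, level and population are all open. Population matters because the primary set is only part of those randomized: 435 of 570 by the protocol's own attrition figures. In that subset a baseline difference need not be chance.

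"Baseline" is also loose. Under Protocol VII.E.6, blood pressure and weight are measured at the Baseline visit and again at the randomization visit, after the cessation sessions. Self-quitters have the two visits combined (VII.E.19). The chloride "baseline" is collected at home after randomization.

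**Working it through.** **Plan's own figures.** n per group = 2(z₀.₉₈₇₅ + z₀.₈₀)²(SD/δ)², with z values 2.2414 and 0.8416, so the squared sum is 9.505.

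- SBP: 2 × 9.505 × (14.5/5.3)² = 142.3, so 143 (stated 144).
- DBP: 2 × 9.505 × (9.4/3.4)² = 145.3, so 146 (stated 147).
- Weight: 2 × 9.505 × (5.0/2.0)² = 118.8, so 119 (stated 120).

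The figures reproduce to within one participant. They rest on change scores without extra covariates, so the covariate rule does not touch them.

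**Entry of a true predictor.** In simulation (3 × 190 randomized, about 145 per arm analysed, 15 candidates screened by one-way ANOVA at an assumed 5%, retention unrelated to the predictor), a given predictor enters in 4.8 to 5.3% of trials, whichever population is screened. At least one of 15 independent candidates enters in 1 − 0.95¹⁵ = 54% of trials. Entry is not harm in itself, but it shows that the final model is often not the fixed one.

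**Precision, by formula.** With baseline/follow-up correlation ρ and equal SDs, change SD = σ√(2(1−ρ)) and ANCOVA residual SD = σ√(1−ρ²). So residual SD = change SD × √((1+ρ)/2), and a predictor explaining R² of the remainder multiplies this by √(1−R²). For SBP at ρ = 0.5: 14.5 × √0.75 = 12.56, and with R² = 10%, 12.56 × √0.90 = 11.91. Power is by noncentral t, 145 per group, two-sided 0.025. Both ρ and R² are assumptions; the documents give neither.

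| Endpoint, ρ | R² 0 | 2% | 10% | Gain (points) |
|---|---|---|---|---|
| SBP, 0.5 | 90.9 | 91.5 | 93.7 | 0.6 to 2.8 |
| SBP, 0.7 | 86.9 | 87.6 | 90.3 | 0.7 to 3.4 |
| DBP, 0.5 | 90.3 | 90.9 | 93.2 | 0.6 to 2.9 |
| DBP, 0.7 | 86.1 | 86.8 | 89.7 | 0.7 to 3.6 |
| Weight, 0.7 | 92.5 | 93.0 | 94.9 | 0.5 to 2.4 |
| Weight, 0.9 | 89.2 | 89.8 | 92.3 | 0.6 to 3.1 |

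**Precision under the rule, by simulation.** SBP power (%) for R² of 2/5/10%, 19,000 trials per scenario, Monte Carlo SE about 0.25 points:

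| Model | ρ = 0.5 | ρ = 0.7 |
|---|---|---|
| Baseline and site only | 90.6 / 90.6 / 90.7 | 86.4 / 86.4 / 86.6 |
| Significance rule | 90.5 / 90.6 / 90.8 | 86.2 / 86.6 / 86.7 |
| Predictor named | 91.2 / 92.2 / 93.7 | 87.0 / 88.2 / 90.1 |

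The rule gains nothing over no extra covariate. Naming the predictor gains 0.7 to 3.4 points over the rule.

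**Type I error.** With retention unrelated to the predictor, a separate simulation of mechanical use (10 candidates) gave omnibus error of 4.5% and 4.1% against 5%. Taking the smallest p-value of 13 models the text would allow raises pairwise error only from 2.5% to 2.9%.

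Now suppose that retention depends on a predictor differently by arm, leaving an imbalance of d SD in the abstinent subset. With no adjustment for that predictor, the test statistic shifts by about d√R²/√(2/145), where √(2/145) = 0.117. At a nominal 2.5%:

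- d = 0.07, R² = 10%: shift 0.19, error about 2.8%.
- d = 0.11, R² = 10%: shift 0.30, error about 3.1%.
- d = 0.23, R² = 2%: shift 0.28, error about 3.1%.
- d = 0.23, R² = 10%: shift 0.62, error about 5.5%.

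The value d = 0.23 comes from retention log-odds slopes of −0.5 per SD in one arm and +0.5 in the others. Simulating the last case gives 5.3% with no extra covariate, 4.8% with the rule screened in all randomized participants, and 2.4% with the rule screened in the abstinent subset.

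**The case against.** The strongest reply is that little is at stake. Power with baseline adjustment is already 86 to 91% for blood pressure under the assumed correlations, against a target of about 80%. The larger gains need R² of 10% beyond baseline, for which the documents give no evidence. This stands, and it limits the point to modest precision and an open model.

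A reader might infer that the rule inflates type I error. The documents do not support that. Error near 5% appears only when a strong predictor drives retention in opposite directions by arm, which no section suggests. Even then it comes from restricting the analysis to abstinent participants with data, since it is largest with no covariate rule at all. Screening the abstinent subset, a natural reading because the rule follows the restriction, would be protective in that case.

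A reader might also infer that covariates were, or will be, chosen with results in hand. Protocol VII.A.4 says that data collection is complete and analysis remains; it does not say whether outcomes by arm had been seen.

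Finally, any specific list involves judgement. Protocol I.6, A.2 says that "body weight is the strongest single predictor of BP", but this is background and does not show what weight adds once baseline blood pressure is in the model. Nothing in the documents supports antihypertensive use as a predictor of weight, diet, chloride or activity. The named list should therefore differ by endpoint.

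**Conclusion.** The point holds as one that should be fixed, not as one that threatens the trial. Beyond baseline value and site, the plan states a method of covariate choice that selects on the wrong property, and it leaves candidates, test, level and population open. The cost is about 0.6 to 3.6 points of blood pressure power (about 0.5 to 3.1 for weight) if one predictor explains an assumed 2 to 10% of variance beyond baseline, plus a final model unknown until the data are tested. Sample size is unaffected.

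These figures use the protocol's sizing test at 0.025, not the omnibus-then-LSD sequence planned for analysis. They also rest on assumed correlations, R², a 5% screen and, for the SBP rule comparison, 15 candidates. Which population is screened matters materially only in the opposite-direction retention case, and no covariate choice repairs an unmeasured driver of retention.

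**What to change.** In the SAP Overview and Protocol XI.1, replace the clause on significantly differing variables, in both the primary and the secondary paragraph, with a list named for each endpoint on prognostic grounds:

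- **Blood pressure models:** baseline value, study site, baseline antihypertensive use (yes/no) and baseline body weight.
- **Weight and secondary endpoints:** baseline value and study site, plus any predictor that the sponsor can justify and list.

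Keep the imbalance-adjusted model only as a sensitivity analysis, with its candidates, test, level and tested population stated.

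Add one line on which visit supplies baseline blood pressure and weight, including for self-quitters' combined visit. Note that the chloride baseline is collected after randomization, so that adjusting for it needs caution.

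Because data collection is complete, state whether outcomes by arm had been seen when the list was fixed.

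The cost is two sentences in each document, a few lines on baseline, and one sensitivity analysis. The two added blood pressure covariates are already collected and use 2 of about 430 degrees of freedom. If outcomes by arm had been seen, the list is less credible and should be labelled as fixed after the data.
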